## **1 Introduction**

**A.** Parents asked to enroll their infant in neonatal research commonly report significant stress around this decision and challenges building relationships with the research team. These issues are likely worse for under-represented populations, which are less likely to be included in neonatal research. This study aims to pilot test an intervention designed to improve the experience for parents asked to enroll in neonatal research, with a special focus on the concerns that arise for those from under-represented populations. This is necessary to improve parental experiences of recruitment, decrease disparities in the research population, and ultimately produce a more generalizable knowledge base within neonatology.

## **2 Brief Overview of the Study Protocol**

**A.** The goal of this study is to pilot test the feasibility of implementing a modified recruitment approach, the Better Research Interactions for Every Family (BRIEF) Intervention, within a neonatal clinical trial. This intervention has two distinct aims: 1) improve the experience for parents asked to enroll their infant in a neonatal clinical trial; 2) decrease disparities in enrollment within a neonatal clinical trial. We will apply the BRIEF Intervention within a single site neonatal randomized control trial (RCT), the Darbe plus IV iron study, using pre/post approach. The objectives of this current ancillary study are to assess feasibility, gain preliminary experience to drive further refinement, and provide effect estimates for a future RCT of the BRIEF intervention.

This study is an ancillary study to the Darbe plus IV Iron study, which is a phase II RCT aiming to demonstrate the feasibility and potential benefit for darbepoetin plus slow-release intravenous iron to decrease transfusions, maintain iron sufficiency, and improve neurodevelopmental outcomes of preterm infants. In the BRIEF study, we will pilot a research team educational module to support recruitment for this neonatal clinical trial.

## **3 Study Staff Responsibilities**

## **4 Study Flow Diagram**

[figure not shown]

Figure 1. BRIEF Study Timeline

[figure not shown]

Figure 2. BRIEF Participant Timeline

## 5 Recruitment and Retention Plan Screening and Eligibility Criteria

## **5.1 Screening Log**

- A. See Screening Log [redacted]**

## **5.2 Eligibility Criteria**

### **A. Inclusion Criteria**

- a. P1:** Infants born between 24-0 and 31-6 weeks of gestation cared for in the UW NICU who are eligible for participation in the Darbe plus IV iron study.
- b. P2:** English or Spanish speaking parents or legally authorized representatives (LARs) who were approached for participation in the Darbe plus IV iron study. Parents/LARs under age 18 will be excluded.
- c. P3:** Parents/LARs who chose to participate in the survey in P2 and shared their contact information indicating interest in participating in an interview.
- d. P4:** English or Spanish speaking parents/LARs who were approached for participation in the Darbe plus IV iron study.
- e. P5:** Research team members who participate in recruitment procedures (e.g., tracking of potential participants, informed consent discussion) for the Darbe plus IV iron study.

## **6 Informed Consent**

### **6.1 HIPAA Authorization**

- A. See HIPAA Authorization document [redacted]**

## **7 Study Interventions**

### **7.1 (P1) Infant Data Extraction**

#### **A. Data Extraction**

- a. [Redacted]** to collect data from DIVI study screening log and EMR and enter in *REDCap BRIEF P1. data extraction* (<https://redcap.iths.org/surveys/?s=K37XKN4DCKWHFNY8>)
  - a.** [redacted] to also collect at discharge—plan to cluster once monthly

### **7.2 (P2) Parent Survey**

#### **A. Survey Distribution**

- a.** DIVI study team to distribute BRIEF P2. survey flyer summary sheet [double sided English/Spanish] at time of recruitment
- b.** REDCAP: emails full team with each entry of parent survey
  - i.** If completed, REDCap automated message notifying [redacted]/[redacted]/[redacted] for incentives and interviews
- c.** [redacted] inform [redacted] and [redacted] if survey NOT completed at 7-10 days (postnatal only) → then [redacted] or [redacted] to bring BRIEF P2. survey flyer summary sheet to patient bedside

#### **B. Incentives**

- a.** Within 3 days of completion of parent survey, [redacted] [or [redacted]/[redacted]] to send out incentives with thank you email to

parents who have completed *REDCap BRIEF P2. family survey* and *REDCap BRIEF P2. family survey Spanish*

- i. Codes for \$25 Amazon or Tango gift card can be found in [AmazonGiftCodes-111-8287595-4521800 – first 10 eGift Cards only]
- ii. Track sent incentives using ORF-004-01 Research Participant Gift Card Tracking Log
  1. Information needed includes Date (gift card dispensed), Participant's Full Name, Gift Card Amount Issued, type of Gift Card (i.e., Amazon or Tango)

**C. Tracking**

- a. Note progress/completion in BRIEF Recruitment Logs
- b. Track enrollment rates

### **7.3 (P3) Parent Interviews (N=40)**

**A. Recruitment**

- a. [redacted]/[redacted] to identify parents who volunteered to participate in *REDCap BRIEF P2. family survey* and *REDCap BRIEF P2. family survey Spanish*
  - i. Select participants for outreach based on purposive sampling criteria:
    1. Equal proportion of enrollees (n=20) and decliners (n=20) in DIVI study
    2. Equal proportion of parents approached pre- (n=20) and post-BRIEF (n=20) Intervention
    3. Within each cohort, aim for at least 50% not non-Hispanic White
    4. For Spanish interviews, aim to recruit at least 8, but as many as 12, out of the 40 total interviewees
  - ii. In order to reach the above goals, prioritize:
    1. All decliners
    2. All not non-Hispanic white participants
    3. Parent/child on Medicaid

Parent Interview Cohorts		
	Pre-BRIEF Intervention	Post-BRIEF Intervention
Enrollees	10	10
Decliners	10	10

**B. Scheduling**

- a. [redacted]/[redacted]/[redacted] to contact selected participants at least 3 days and up to no more than 4 months post-survey completion to participate in an interview; refer to participant's preferred method of contact
  - i. If by email:

- 1. Provide overview of interview
- 2. Attach BRIEF P3. parent interview information sheet
- 3. Provide potential dates and times for interview
- ii. If by phone:
  - 1. Provide overview of interview
  - 2. Review BRIEF P3. parent interview information sheet, time permitting
  - 3. Schedule interview
  - 4. Email BRIEF P3. parent interview information sheet immediately after the call
- iii. If by text:
  - 1. Introduce self and BRIEF study
  - 2. Remind participant about BRIEF P3. parent interview information sheet
  - 3. Provide potential dates and times for interview
- iv. Update the BRIEF Recruitment Logs spreadsheet with scheduled date and time

#### C. Reminders

- a. [redacted]/[redacted]/[redacted] to email/call/text participant to remind them of the interview the day before (confirm preferred method of contact during scheduling)
  - i. Send multiple reminders depending on how far out the interview is scheduled, or if the parent prefers multiple reminders

#### D. Interview

- a. Connect to Zoom call prior to scheduled interview time
- b. Request permission to record Zoom call
  - i. If yes, begin recording
  - ii. If no, take notes of participant's responses during interview
- c. Review information from BRIEF P3. parent interview information sheet; if necessary
- d. Begin interview
- e. Stop recording
- f. Collect information necessary to send interviewee incentive (i.e., interviewee's email)
- g. Note completion of the interview in BRIEF Recruitment Logs
- h. Upload interview audio to shared drive

#### E. Incentives

- a. [redacted]/[redacted] to send out incentives with thank you email to parents who have completed Parent Interview
  - i. Track sent incentives using ORF-004-01 Research Participant Gift Card Tracking Log
    - 1. Information needed includes Date (gift card dispensed), Participant's Full Name, Gift Card Amount Issued, type of Gift Card (i.e., Amazon or Tango)

#### 7.4 (P4) Recruitment Discussion (N=100)

**A. Audio-recording and upload (N=100)**

- a. DIVI team has script for consent to audio-record consent discussion**
- b. DIVI team member to retrieve iPad from [redacted]**
  - i. iPad will be passcode protected**
  - ii. Passcode will be provided to consenting DIVI study team members only**
- c. Once the tablet is unlocked, two icons will be present on the home screen**
  - i. Voice Memos app**
  - ii. Link to REDCap**
- d. Using the Voice Memos app**
  - i. Open Voice Memos app**
  - ii. Tap the record button (red circle) to begin recording**
  - iii. Tap the pause button (two vertical red bars) to stop recording**
  - iv. Tap “Done” to save the recording**
  - v. Renaming the recording**
    - 1. Tap the name at the top of the screen (the default name is typically “New Recording X”)**
    - 2. Enter the [DIVI screening ID]**
    - 3. Tap “return” on the keyboard**
    - 4. Tap “Done” on the bottom right corner of the screen**
  - vi. Tap the more options button at the top of the screen (Circle with three dots)**
  - vii. Tap “Share...”**
  - viii. Tap “Save to files”**
  - ix. Tap “On My iPad”**
  - x. Select “BRIEF Consent Audio”**
  - xi. Tap “Save”**
- e. Return to home screen and open link to REDCap survey**
  - i. Enter DIVI screening ID**
  - ii. Select your name from the list of DIVI Team Members**
  - iii. If the Consent Discussion was recorded, select “Yes”**
  - iv. Tap “Upload file”**
  - v. Tap “Choose File”, tap “Choose File” again**
  - vi. Navigate to the “BRIEF Consent Audio” folder**
    - 1. If not in the BRIEF Consent Audio folder already, tap “Browse” in the upper left-hand corner**
    - 2. Tap “On My iPad”**
    - 3. Tap the “BRIEF Consent Audio” file**
    - 4. Tap the recording**
  - vii. Tap “Upload file”**
  - viii. Complete short milestones format survey about consent discussion that just took place**
- f. Close both the Voice Memos and the REDCap link and turn off the tablet**
- g. Return tablet to [redacted]**

**B. Milestone self-assessments (N=100)**

- a. Complete the Likert Scale questions for each of the 11 milestones
- b. Close survey
- c. [Automated REDCAP step]—share with BRIEF team with each completion
- d. Close both the recording app and the REDCap link and turn off the tablet
- e. Return tablet to [redacted]

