Better Research Interactions for Every Family

Statistical Analysis Plan

Project # 3469

[name]

6/1/2022

A feasibility study for an educational intervention to improve equity and respect in recruitment conversations with families who are eligible for a neonatal clinical trial. A pre-post study design will be used. Approximately 200 parents of eligible infants will be approached for consent, half using the current recruiting protocol ("pre") and half using the novel intervention ("post"). Conversations will be administered by 6 members, some of whom will administer more conversations than other members.

A subsample of these conversations will be recorded (n_record). This will be split equally between "pre" and "post" periods. Each recorded recruitment conversation will then be assessed by 3 experts (2 independent, and the member who administered the educational content). They will fill out a questionnaire (approximately 15 questions) answered with a Likert score. These questions fit into logical groupings to assess different aspects of equity and respect during the recruitment conversation.

The number of observations will be the number of conversations recorded multiplied by 3 (n_record*3). There are several sources of correlation between these observations (recruitment conversation, member administering the recruitment conversation, expert making the assessment) and so GEE will be used to estimate the intervention effect on each question and test the null hypothesis of no effect.

Analysis Plan

Descriptive statistics will be used to summarize eligible parents who engaged in conversations. Frequencies and percentages will be reported as appropriate for categorical variables. Means, medians, and standard errors will be calculated for continuous variables. Outcomes (5-point Likert scale) will be summarized in each intervention arm at the question level, as a total across all questions, and totals within each pre-defined question subgroup.

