At the question level, ordinal logistic regression will be used to assess the effect of the intervention on the distribution of scores. Models will be fit using generalized estimating equations (GEE) to account for correlation among results assessed on the same conversation. Results will be reported as intervention odds ratios and 95% confidence intervals. To test the overall effect of the intervention on the score (and in each subgroup of questions) we take the total of the question scores to be continuous and use GEE to fit standard linear regression to test the mean effect of intervention.

Models above assume each conversation administer has the same mean outcome and that experts evaluate themselves the same as others. These two assumptions will be evaluated and GEE models adjusted as needed. Further, since we plan to run many statistical tests (15 questions individually, score totals, subgroups), the p-value threshold to determine significance will be adjusted using Holm's method to control the family-wise type I error rate.

List of Figures/Tables

Figure 1: Flow diagram showing sample size allocation in pre/post cohort, exclusion, and number of videos sampled for assessment.

Figure 2: Distributions of scores in pre/post cohorts for each question, question totals and subgroups.

Figure 3: Estimated odds ratios and confidence intervals and of the pre/post effect tested for each question.

Table 1: demographics of those approached vs videos sampled.

Table 2: Likert score outcomes (counts, percentages) in pre/post, intervention odds ratio, 95% CI's and p-values for each question.

Table 3. Outcome totals (Mean, SD, IQR) and subgroups, estimates of mean effects (95% CIs) .

Power calculations

To assess statistical power, we pair simulation with calculations based on cluster randomized trial designs with a continuous outcome. These equations assume a mixed effects model consistent with the GEE methods used above and depend on the assumed effect size, outcome standard deviation, and intra-cluster correlation. To achieve 80% power at a 0.05 level when the true mean difference is 5 and standard deviation of 5, 8 videos (with 3 observations) need to be recorded per trial arm ($8*3*2 = 48$ total observations) if the intra-recording correlation is low ($\rho = 0.1$) while 15 recordings are needed per trial arm ($15*3*2 = 90$ total observations) if intra-recording correlation is high ($\rho = 0.8$).

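### Recruiters' self-assessments go automatically to the BRIEF team before the experts score the same recording, and nothing in the plan keeps raters from seeing them

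*Protocol*

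**What the plan says.** Protocol 7.4A describes one REDCap session straight after the consent discussion. The recruiter enters the DIVI screening ID, is told to "Select your name from the list of DIVI Team Members", uploads the audio, and must then "Complete short milestones format survey about consent discussion that just took place". Protocol 7.4B gives the content of that survey, "Complete the Likert Scale questions for each of the 11 milestones", and follows it with an automated step: "share with BRIEF team with each completion".

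The SAP's opening description has each recorded conversation subsequently "assessed by 3 experts (2 independent, and the member who administered the educational content"). Its Analysis Plan section names as a modelling assumption, to be evaluated, that "experts evaluate themselves the same as others". The design is not randomised: "A pre-post study design will be used".

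Separately, for the parent survey, Protocol 7.2A says that REDCap "emails full team with each entry of parent survey". It does not say whether that email carries the answers.

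**The concern.** The expert ratings are the outcome of the SAP's comparison. They are useful as an assessment of the recruiters only if they are made independently of the recruiters' own view of how the conversation went. The Protocol writes in a step that releases that view, tied to a recording and a recruiter, before the experts score. This is more than a missing sentence on masking, because a specific routing instruction creates the pathway.

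Three things are at stake:

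- **Bias.** A rater who knows the self-score may move towards it. If self-scores change between periods differently from what the rater would have recorded unaided, the difference enters the estimated effect. GEE allows for correlation between ratings but does not remove a shift of this kind, and a pre/post design has no randomised comparison to offset it.
- **Precision.** Shared information can make ratings of one recording more alike and so raise the intra-recording correlation.
- **The SAP's own check.** If raters of other people's conversations have seen the self-scores, self-ratings and ratings by others may converge. The assumption under test could then look satisfied when it is not.

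The pilot is meant to supply effect estimates for a later RCT, so a distortion would carry forward.

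**Working it through.** **1. Order of events.** In Protocol 7.4A the audio upload and the milestone survey are consecutive steps of one session. The release in 7.4B follows completion of that survey. The SAP places expert assessment after recording. The self-assessment therefore exists, and has been released, before expert scoring in the ordinary course.

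**2. Can it be linked to a recording?** Yes. The session holds the screening ID, the recruiter's name and the audio file.

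**3. Does a rater receive it?** The documents do not list the BRIEF team. The third rater delivered the educational content, and Protocol section 2 describes the BRIEF study as piloting that educational module, so membership is plausible but not stated. Nothing places the two raters called independent on the team.

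**4. Is there a safeguard?** Neither document has a rule that masks raters to self-assessments or locks their scores first. Protocol 9.3 and section 10 are headings without text, and 9.2 refers to study forms on a shared drive that is not part of these documents. A rule could exist there.

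**5. Direction and size of bias.** Let R be the score a rater would give unaided, S the self-score, and w the fraction by which an exposed rater moves towards S, taken as equal in both periods. The recorded score is R + w(S − R). If R changes by d and S by s from pre to post, the recorded change is d + w(s − d).

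- Bias per exposed rater = w(s − d).
- Averaged over three raters, of whom e are exposed: bias = (e/3) × w(s − d).
- Taking d = 5, the SAP's planned difference: s = 5 gives w(5 − 5) = 0; s above 5 gives an upward bias; s below 5 gives a downward bias.

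The documents give no value for w, s or e. The self-assessment has 11 milestones and the expert questionnaire about 15 questions, and the two scales are not equated. The bias therefore cannot be computed.

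**6. Precision, starting from the SAP's own figures.** Inputs from the SAP's power section: difference 5, SD 5, three ratings per recording, 80% power, level 0.05 (two-sided assumed). With k recordings per arm and correlation ρ, the design effect is 1 + 2ρ and SE = 5 × √[2(1 + 2ρ)/(3k)].

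- Normal approximation: 2 × (1.960 + 0.842)² ≈ 15.70 observations per arm before the design effect. At ρ = 0.1, 15.70 × 1.2/3 = 6.28, so 7 recordings. At ρ = 0.8, 15.70 × 2.6/3 = 13.60, so 14.
- Noncentral t with 2(k − 1) degrees of freedom: 8 recordings (power 83.6%) and 15 (power 81.0%). These are the SAP's figures exactly.

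Power by the same t calculation, with the ρ values above 0.8 assumed to show a range:

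| ρ | 8 per arm | 15 per arm | Needed per arm |
|---|---|---|---|
| 0.1 | 83.6% | – | 8 |
| 0.8 | 51.6% | 81.0% | 15 |
| 0.9 | 48.7% | 78.1% | 16 |
| 1.0 | 46.1% | 75.3% | 17 |

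The loss is material only if few recordings are scored. Protocol 7.4 gives N = 100 recordings. If all were scored, 50 per period, then even at ρ = 1 the SE is 5 × √[2 × 3/(3 × 50)] = 1.0. The planned difference is then 5 standard errors, against about 2.80 needed for 80% power.

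**The case against.** The strongest reply is that exposure of a rater is inferred. No list of BRIEF team members or alert recipients is given. The SAP calls two raters independent. Its remark about experts evaluating themselves suggests that an expert sometimes rates a conversation that he or she conducted. For that conversation the rater is the source of the self-score and is not exposed to someone else's view. This stands as a limit on what can be claimed. It does not close the pathway, because the question then passes to the other raters of that recording.

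It can also be said that this is a feasibility pilot and that prompt access to self-assessments helps the team refine the intervention. That is a fair reason for someone on the team to see them early, but not for a rater to see them before scoring.

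Two stronger readings are tempting, and the documents do not support them:

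- A reader might infer that raters also see parents' opinions through the full-team email. Protocol 7.2A may describe only a notification: the item beneath it is a message for incentives and interviews, and the survey's content is not given.
- A reader might infer that the effect is inflated, by a known share of the planned 5 points. Step 5 of the working shows that the sign depends on s − d and that none of the inputs is available.

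**Conclusion.** The point holds as a weakness in a written procedure. Identifiable self-assessments are released to the BRIEF team ahead of expert scoring, and the plan contains no masking or locking rule. Whether any rater is a recipient is a reasonable inference for the one who delivered the education, and unsupported for the two called independent. The consequence for the pre/post estimate may go either way or be nil, and its size cannot be derived from the documents. The precision cost is bounded by the table in the working: appreciable with 8 to 15 recordings per arm, and negligible for the planned difference if about 50 per arm are scored. How far sharing would raise ρ is unknown. The change should be made because it costs little and the ratings cannot be made blind afterwards. If no rater is on the distribution and none has other access to the self-assessments, a sentence saying so would largely settle the matter.

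**What to change.** - **Protocol 7.4B.c:** make the automated message a completion notice without answers, addressed to coordinators who do not rate recordings.
- **Protocol 7.4 and the SAP's opening description:** state who the raters are, and that no rater sees another person's self-assessment of a recording until his or her own scores for it are entered and locked. The wording is confined to another person's self-assessment because recruiters write their own, and locking cannot mask a recruiter who also rates to a score that he or she gave.
- **Protocol 7.2A.b:** as a precaution, specify that the full-team email is a notice without survey answers.

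The cost is two REDCap alert settings and a short addition to the text. The downside is that the BRIEF team sees self-assessment feedback later.

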### **7.5 (P5) Research Team Member Interviews (N=8)**

- F. Scheduling**
  - a. [Redacted] to invite NICU team members to complete a scheduling poll
  - b. [Redacted] to schedule NICU team members based on responses to scheduling poll
- G. Reminders**
  - a. [Redacted] to email NICU team member to remind them of the interview the day before
    - i. Send multiple reminders depending on how far out the interview is scheduled, or if the NICU team member prefers multiple reminders
- H. Interview**
  - a. Connect to Microsoft teams call prior to scheduled interview time
  - b. Request permission to record Microsoft teams call
    - i. If yes, begin recording
    - ii. If no, take notes of participant's responses during interview
  - c. Begin interview
  - d. Stop recording
  - e. Collect information necessary to send interviewee incentive (i.e., interviewee's email)
  - f. Note completion of the interview in BRIEF Logs
  - g. Upload interview audio to shared drive
- I. Incentives**
  - a. Upon completion of interview send out incentive via Tango
    - i. Track sent incentives using ORF-004-01 Research Participant Gift Card Tracking Log
      - 1. Information needed includes Date (gift card dispensed), Participant's Full Name, Gift Card Amount Issued, type of Gift Card (i.e., Amazon or Tango)

